7.7. Tumor Assessment

Tumor imaging (CT or MRI, with preference for CT) will be performed at screening and every 8 weeks (± 7 days) from Cycle 1 Day 1 until disease progression. Any evaluable disease must be documented at screening and reassessed at each subsequent tumor evaluation. At the investigator's discretion, CT scans may be repeated at any time if progressive disease is suspected. An objective response is considered confirmed once repeat assessments ≥ 4 weeks after initial documentation are available.

A CT scan or MRI of the thorax, abdomen, and pelvis plus other relevant evaluations as appropriate, including bone scan for patients with bone metastasis, will be performed to assess all known disease. All known disease must be documented at baseline as target or non-target lesions using RECIST v1.1. The CT scan will be used for the evaluation criteria RECIST v1.1 by the investigator at each study center. Routine use of positron emission tomography (PET) scans should not be used to assess radiologic response to treatment for this study.

Unless contraindicated, intravenous contrast product must be used to maximize visualization of all lesions. Patients who are at increased risk of allergic reaction to iodinated contrast media should not have enhanced CT, but should instead be provided magnetic resonance imaging (MRI) with gadolinium enhancement patient per local protocol, with mandatory imaging coverage from thoracic inlet to symphysis pubis plus unenhanced CT scanning with coverage from the thoracic inlet to the inferior costophrenic recess. Patients with bone pain or biochemical changes suggestive of bony disease without other clear explanation should have a bone scan at baseline and if bone metastases are documented should then have bone scans or other appropriate imaging examinations as clinically indicated.

The same imaging technique should be used on the same patient throughout the study.

After first documentation of response (CR or PR), imaging performed at the next regularly scheduled timepoint may be used for response confirmation.

Patients who permanently discontinue study drugs prior to progressive disease will continue with regular tumor assessments as per protocol every 8 weeks (± 7 days) until disease progression, administrative issues, start of other anticancer therapy or any other reason listed in [Section 8.4](#), whichever occurs first. This imaging schedule will be maintained regardless of any intermediate unscheduled scans. Patients who withdraw from the study for clinical or symptomatic deterioration before objective documentation of progressive disease will be requested to undergo appropriate imaging to confirm progressive disease. Every effort will be made to confirm a clinical diagnosis of progressive disease by imaging.

All efforts will be made to ensure that the imaging equipment, contrast agent, and person (investigator or radiologist) performing the evaluation is kept constant throughout a patient's course on study.

7.8. Pharmacokinetics of Pamiparib and Temozolomide

Blood will be collected to characterize the PK of both pamiparib and temozolomide. Additionally, blood may also be used to explore the presence of metabolites in a qualitative or semi-quantitative manner.

Blood sampling for PK will be collected at the timepoints specified in [Schedule](#) of Assessments ([Appendix 1 Table 1](#)).

Details concerning handling of the PK plasma samples, including labeling and shipping instructions will be provided in the Study Manual.

Samples will be shipped to the central laboratory where they will be stored and batch shipped to the designated bioanalytical laboratory for quantification of plasma pamiparib and TMZ concentrations using a validated method.

7.8.1. PK of Pamiparib

To better characterize the pamiparib PK profile prior to TMZ administration, the first 15 patients enrolled into the study in dose escalation will undergo intensive PK sampling starting on Day -2 at the following timepoints: pre-dose (within 30 min prior to dose), 30 minutes (± 5 min), 1 hour (± 15 min), 2 hours (± 30 min), 4 hours (± 30 min), 6 hours (± 30 min); 24 hours (± 2 hours) post-dose on Day -1; and 48 hours (± 2 hours) post-dose on Day 1 as detailed in Table 2 of [Appendix 1](#).

After 15 patients have completed intensive PK sampling, all other patients enrolled in dose escalation and expansion will have PK samples collected at the following timepoints: pre-dose (within 30 min prior to dose), 1 hour (± 15 min), 2 hours (± 30 min), and 4 hours (± 30 min) post dose on both Cycle 1 Day 1 and Cycle 1 Day 15. The time of study drug administration on the day prior to Cycle 1 Day 15 must be recorded on the eCRF. Details concerning collection and handling of the PK plasma samples will be provided in the Study Manual.

7.8.2. PK of TMZ

Pharmacokinetic samples will be collected from patients in all cohorts at the following timepoints: pre-dose (within 30 min prior to dose) and 1 hour (± 15 min) post dose on Cycle 1 Day 1 and Cycle 1 Day 7. The time of study drug administration on the day prior to Cycle 1 Day 7 must be recorded on the eCRF.

7.9. Biomarker Assessments

The biomarker analysis includes but it is not limited to germline *BRCA1/2* mutation, HRD status, and somatic mutation analysis. Blood and biopsies for biomarker analysis will be collected at the timepoints specified in [Schedule](#) of Assessments ([Appendix 1 Table 1](#)).

7.9.1. Blood for biomarker analysis

All patients will provide blood samples for analysis of baseline germline *BRCA* and/or other mutations.

All patients will also provide blood samples to be processed into serum, plasma, and cell fractions for the analysis of germline mutations, and circulating markers, such as, but not limited to, circulating nucleic acids (CNA).

7.9.2. Tumor tissues for biomarker analysis

Patients from Dose Escalation, patients from Dose Expansion Cohorts 1-3 with known HRD or BRCA mutation status and patients from Dose Expansion Cohorts 4 and 5

An archived, formalin-fixed, paraffin-embedded tumor sample will be collected from all patients, if available, for retrospective analysis of HRD mutational status. Archival tumor tissue shall be sent to the central laboratory for biomarker testing (either a formalin-fixed, paraffin-embedded block with tumor tissue [preferred] or approximately 10 unstained slides). The most recent tumor block is preferred.

In the absence of archival tumor tissues, a fresh baseline biopsy of a tumor lesion is highly recommended. Written patient consent is required for fresh tumor biopsies.

An optional biopsy will also be taken at the EOT visit for the patients who have confirmed disease progression from accessible tumor sites. These samples will be used to explore resistance mechanism(s). If feasible, any follow up biopsy should be from the same tumor lesion as the baseline biopsy. Written patient consent is required for fresh tumor biopsies.

Fresh biopsies should be limited to readily accessible tumor lesions (e.g., skin, peripheral lymph nodes, lung, liver, or internal lymph node metastases which can be readily accessed using CT guidance). If performed, a tissue cylinder should be obtained that has proper size for histological examination and biomarker analysis.

Patients from Dose Expansion Cohorts 1-3 with unknown BRCA 1/2 mutation or HRD status and Cohort 6

All patients who are potential candidates for enrollment on these cohorts must provide a mandatory archival tumor tissue sample (either a formalin-fixed, paraffin-embedded block with tumor tissue [preferred] or approximately 10 unstained slides) for central prospective testing of HRD status in order to determine their eligibility. The most recent tumor block is preferred. If no archival tumor tissue is available, a mandatory fresh tumor biopsy should be performed. Written patient informed consent is required for archival tissue or biopsy collection (prescreening informed consent).

Any tissues taken during pre-screening period will not be re-collected at screening or Cycle 1 Day 1.

7.9.3. Optional tumor biopsy for pharmacodynamics analysis (Dose Escalation and Dose Expansion Cohorts 1-5)

An optional biopsy for pharmacodynamics at Cycle 1 Day 1 and Cycle 1 Day 15 is highly recommended. If feasible, any follow up biopsy should be ideally taken from the same tumor lesion as the baseline biopsy.

Instructions for the processing, storage, and shipping of samples will be provided in the Study Manual.

7.10. Appropriateness of Measurements

All safety, PK, and tumor assessments used in this study are standard, i.e., widely used and generally recognized as reliable, accurate, and relevant. PK and PD assays will be performed using validated GLP methods.

8. STUDY VISITS AND FOLLOW-UP

8.1. Prescreening (Dose Expansion Only, Days -84 to -29 prior to Screening)

During the dose expansion phase of the study, patients in the Expansion Cohorts 1 to 3 (ovarian, TNBC, and mCRPC, respectively; see Section 5.1) who have unknown biomarker status will undergo pre-screening for evaluation of HRD status. All patients in the Dose Expansion Cohort 6 will undergo prescreening for central evaluation of HRD status. A separate pre-screening informed consent must be obtained.

An archival tumor sample is acceptable; however, if not available, a fresh tumor biopsy must be obtained for HRD testing.

The following will be performed during the pre-screening visit:

- Obtain written informed consent from the patient to perform a tumor biopsy if it is required for the purpose of meeting the eligibility of the study
- Prepare tumor samples and ship to the qualified central lab for mutation analysis as specified in the Study Manual

8.2. Screening Period (Day -28 to Day -1)

A signed, written informed consent must be obtained prior to screening assessments and before any study-specific assessments are initiated. Results of standard-of-care tests or examinations performed prior to obtaining informed consent and within the screening windows may be used and do not need to be repeated as long as they meet protocol specifications. The study-specific assessments and procedures are shown in the Schedule of Assessments in [Appendix 1 Table 1](#).

Screening Period assessments are the same for the dose escalation and dose expansion phases of the study and will be completed within 28 days prior to the first dose of the investigational product. Some assessments have a narrower screening window as shown in the Schedule of Assessments in [Appendix 1 Table 1](#). Screening assessments obtained within 4 days of Day 1 do not have to be repeated on Day 1.

8.3. Assessments during Treatment Period

Safety assessments should be performed at all visits to the study center and throughout the study.

8.3.1. PK Intensive Visit (Day -2 to Day 1) (Dose Escalation Cohort ONLY)

To better characterize the pamiparib PK profile prior to TMZ administration, the first approximately 20 patients enrolled into the study will undergo intensive PK sampling starting on Day -2 as detailed in [Appendix 1 Table 2](#).

Once 20 patients have completed the pamiparib PK intensive sampling, the remainder of patients will undergo limited PK sampling as detailed in [Appendix 1 Table 1](#). Any modifications to assignment of PK sampling schedule may be implemented following discussion with the Medical Monitor.

Patients who participate in the PK intensive sampling will have baseline assessments performed on Day -2 before pamiparib dosing rather than on Day 1 as detailed in [Appendix 1 Table 2](#).

Note: The collection of blood for the pamiparib PK 48-hour post-dose timepoint must occur **prior** to the administration of pamiparib and TMZ on Day 1.

8.3.2. Cycle 1 (28 days)

During Cycle 1, all assessments (except for PK post-dose blood collection) performed during the clinic visit must be done **prior** to study drug administration. On days with PK assessments, pamiparib (first dose) and TMZ should be administered in the clinic.

For the Dose Expansion Cohorts, a 2-day window is allowed during Cycle 1 visits.

A list of all of the activities during Cycle 1 is found in the Schedule of Assessments Table ([Appendix 1 Table 1](#)).

8.3.3. Subsequent Cycles

A list of all of the activities during subsequent cycles in the first year are listed in the Schedule of Assessments Table ([Appendix 1 Table 1](#)).

All assessments performed during the clinic visits and subsequent cycles must be done **prior** to study drug administration (unless otherwise noted).

8.3.4. Unscheduled Visits

Unscheduled visits may be performed at any time at the patient's or the investigator's request and may include vital signs/physical examination; ECOG Performance Status; AE review; concomitant medications and procedures review; radiographic assessments; physical examination of liver, spleen, and lymph nodes; disease-related constitutional symptoms; and hematology and clinical chemistry laboratory assessments. The date and reason for the unscheduled visit must be recorded in the source documentation.

If an unscheduled visit is necessary to assess toxicity or for suspected PD, then diagnostic tests may be performed based on the investigator assessment as appropriate, and the results of these tests should be entered on the unscheduled visit eCRF.

8.4. End-of-Treatment Visit

Patients who discontinue from study drug for any of the reasons listed below will undergo an EOT visit within 7 days of discontinuation of all study drugs. If routine laboratory tests (e.g., hematology, clinical chemistry) were completed ≤ 7 days before the EOT Visit, these tests do not need to be repeated.

However, the EOT visit may occur later than 7 days after discussion with the Medical Monitor for specific circumstances, such as prolonged hospitalization. If the EOT Visit did not occur until 30 days (± 7 days) or later after the last dose of pamiparib and TMZ, the EOT Visit may also be used as the Safety Follow-up Visit.

Patients with a required EOT visit may discontinue study drug for any of the following reasons:

- Disease progression

- Investigator decision
- Adverse event(s)
- Pregnancy
- Patient withdrew consent for study drug
 - Patients may voluntarily withdraw consent from study drug at any time
 - Patients may continue to participate in the Follow-up Phase, if the patient withdraws consent from the Treatment Phase
- Start of other anticancer therapy
- Patient noncompliance
 - Study site staff should first counsel patients who are significantly noncompliant (e.g., missing 2 treatment cycles) on the importance of study drug compliance and drug accountability. The investigator may, in consultation with the medical monitor, discontinue patients from treatment who are consistently noncompliant

The reason for discontinuation from study drug will be recorded on the eCRF.

All the assessments performed for the EOT visit are listed in the Schedule of Assessments ([Appendix 1 Table 1](#)).

The visit at which the assessment showed progressive disease may be used as the EOT visit provided that all required assessments were performed. A CT does not have to be repeated at the EOT visit if it was performed within 14 days of the visit or at a prior response evaluation that documented progressive disease. ECG does not have to be repeated if it was performed within 14 days of the EOT visit.

8.5. Follow-up Assessments

8.5.1. Safety Follow-Up

All patients who discontinue study drugs will have a safety follow-up approximately 30 days after the last day of study drugs to collect AEs and SAEs that may have occurred after the patient discontinued from the study drugs as well as concomitant medications. The investigator or his/her designee will also contact the patient to collect AE and SAE information as well as any new anticancer therapy given after the last day of study drugs. A laboratory assessment is only required if the patient had an ongoing laboratory abnormality at the previous visit that the investigator considered to be related to study drugs.

8.5.2. Efficacy Follow-Up

Patients who were not discontinued from study drugs due to disease progression and meet criteria otherwise (e.g., discontinued for AE and no new anticancer therapy) will be followed every 8 weeks (\pm 7 days) until disease progression, administrative issues, start of other anticancer therapy or any other reason listed in Section [8.4](#), whichever occurs first.

If the patient refuses to return for these visits or is unable to do so, every effort should be made to contact the patient or patient's guardian by telephone to determine the patient's disease status and survival.

8.5.3. Survival Follow-Up

Patients enrolled during the dose expansion phase of the study will be followed for survival and further anticancer therapy information post progression via phone contact (with the patient's guardian, if applicable) or other means (e.g., clinic visit or review of medical records) approximately every 3 months ([Appendix 1 Table 1](#)).

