- The EOT visit will occur within 7 days after a patient permanently discontinued study drugs for any of the reasons outlined in Section 8.4. A visit should be scheduled as soon as possible, but the EOT visit may occur later after discussion with the Medical Monitor for specific circumstances, such as prolonged hospitalization. The visit at which CT or MRI showed progressive disease may be used as the EOT visit provided that all required assessments were performed. If routine laboratory tests (e.g., hematology, clinical chemistry) were completed ≤ 7 days before the EOT Visit, these tests do not need to be repeated. The CT/MRI does not have to be repeated if it was performed within 14 days of the EOT visit or at a prior response evaluation that documented progressive disease. ECG does not have to be repeated if it was performed within 14 days of the EOT visit. If the EOT Visit did not occur until 30 days (± 7 days) or later after the last dose of pamiparib and TMZ, the EOT Visit may also be used as the Safety Follow-up Visit.
- All patients who permanently discontinue study drugs will have a safety follow-up approximately 30 days after the last day of study drugs to collect AEs and SAEs that may have occurred after the patient discontinued from the study drugs. If the patient does not require any laboratory assessments, the investigator or his/her designee will contact the patient to collect this information. (Protocol Section 8.5.1).
- Following permanent discontinuation of study drugs and/or Safety Follow-up parts of the study, every effort should be made to follow up with all patients by phone every 3 months for their survival status until patient death (Protocol Section 8.5.3).

6. A window of ± 2 days on Cycle 1 Day 7 and Cycle 2 Day 1 is allowed during **Dose Expansion Only**.
7. Complete physical examination includes the following items: 1) general appearance; 2) head, eyes, ears, nose, and throat; 3) neck; 4) heart; 5) chest (including lungs); 6) abdomen; 7) extremities; 8) skin; 9) lymph nodes; 10) cardio-vascular; 11) neurological status.
8. A limited physical examination should be directed at the evaluation of symptoms or specific safety issues. Changes from baseline abnormalities should be recorded at each subsequent physical examination. New or worsening abnormalities should be recorded as AEs if appropriate.
9. A single 12-lead ECG will be performed during Screening within 14 days of Cycle 1 Day 1 and at the EOT visit.

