6 STATISTICAL METHODS

No formal hypothesis testing will be conducted in this study. Data will be described mainly using descriptive statistics. Confidence intervals will be constructed to describe the precision of the point estimates of interest (e.g., objective response rate and disease control rate). Efficacy and safety analyses will be performed by dose escalation and dose expansion phases accordingly. Within dose escalation phase, data will be summarized by dose level within a dosing cohort or all combined. Within dose expansion phase, data will be summarized by cohort.

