6.1 ANALYSIS POPULATIONS

- Safety Analysis Set (SAF): includes all patients enrolled into the study who receive any dose of pamiparib and/or TMZ. The Safety Analysis Set will be used for overall survival analysis and safety analyses.
- Efficacy-Evaluable Analysis Set: includes patients in the SAF who had evaluable disease in the dose escalation phase (or measurable disease in the dose expansion phase) at baseline and had at least one postbaseline tumor assessment unless discontinued treatment due to clinical progression or death prior to tumor assessment.

Evaluable disease means patients may have measurable (target lesions) or non-measurable lesions (non-target lesions); measurable disease means patients must have at least 1 measurable lesion (target lesions) and may or may not have non measurable lesions (non-target lesions).

- DLT Evaluable Analysis Set: includes patients who received $\geq 70\%$ of BGB-290 and TMZ during the DLT assessment window (Cycle 1). Additionally, patients who had a DLT event during the DLT assessment window despite receiving $< 70\%$ of the scheduled dose will also be included.
- PK Analysis Set: includes patients who received any dose of BGB-290 or TMZ, and contributed at least one plasma concentration.

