Kaplan-Meier method will be used to estimate PFS and PFS-6m, and corresponding quartiles (including the median) in the responders. A two-sided 90% CIs of median, Q1 and Q3 will be calculated for each cohorts using generalized Brookmeyer and Crowley method (Brookmeyer & Crowley, 1982). Event free rate at the specified time point (e.g., 3, 6, 9 or 12 months) will be estimated using the Kaplan-Meier method along with the corresponding 90% CI constructed using Greenwood's formula.

- **OS and OS-6m**

OS is defined as the time (months) from the date of the first dose of combination treatment to death due to any cause. Deaths that occur on or before the data cutoff date will be considered as an event. Data from patients who are alive on or before the data cutoff date will be censored at the last known alive date. The OS-6m is defined as the percentages of subjects in the analysis population who remain alive and progression-free at 6 months. The tables for OS and OS-6m will be summarized in SAF.

Kaplan-Meier method will be used to estimate OS and OS-6m, and corresponding quartiles (including the median) in the responders. A two-sided 90% CIs of median, Q1 and Q3 will be calculated for each cohorts using generalized Brookmeyer and Crowley method (Brookmeyer & Crowley, 1982). Event free rate at the specified time point (e.g., 3, 6, 9 or 12 months) will be estimated using the Kaplan-Meier method along with the corresponding 90% CI constructed using Greenwood's formula.

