8 CHANGES IN THE PLANNED ANALYSIS

There are some changes in the planned analysis and they are listed below:

- DLT will be provided in a listing and no descriptive statistics will be provided.
- Subgroup analysis for ORR will only be done for SCLC patients in chemosensitivity and number of prior regimens.
- All by-visit analyses will be removed, and the following will be performed: hematology data will be presented in a shift table and serum chemistry will be provided in a listing. ECG will be listed. A listing of QTcF will be provided for patients with abnormal postbaseline values and abnormal changes from baseline. ECOG and vital signs will be provided in listings.
- Ninety percent CIs will be presented instead of 95% CIs.
- OS analyses will be conducted in SAF instead of Efficacy Evaluable Analysis Set. Only PFS and OS analyses will be conducted and not PFS-6m and OS-6m analyses.
- Efficacy analyses such as ORR, PFS and DOR will be based on radiographic responses or radiographic progression.
- Treatment-emergent SAEs, treatment-related TEAEs, TEAEs with grade 3 or above, and treatment-related SAEs will be summarized by SOC, PT and CTCAE grade. AEs that led

to death and AEs that led to treatment discontinuation, dose reduction or dose interruption will only be listed.

- Number of treatment cycles will not be summarized. Instead, reasons for dose reduction, dose interruption and missed dose will be summarized.

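### The protocol gives two different answers on who is followed for survival, while the SAP analyses OS in all treated patients; under the narrower text, OS in the roughly 50 escalation patients would likely be too long.

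*Protocol*

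**What the plan says.** **Who is followed.** Protocol Section 8.5.3 (Survival Follow-Up) states: "Patients enrolled during the dose expansion phase of the study will be followed for survival and further anticancer therapy information post progression", about every 3 months, and points to Appendix 1 Table 1. Footnote 5 to that table states that "every effort should be made to follow up with all patients by phone every 3 months for their survival status until patient death", and cites Section 8.5.3 as its source. Section 4.1 provides for survival follow-up after the end-of-treatment visit with no limit by phase, but refers to Section 8.5 for the details. The synopsis says the same without that reference. Section 8.7 (End of Study) is not limited by phase either.

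**Other contacts.** Section 8.5.1 gives every patient a safety follow-up about 30 days after last dose. Section 8.5.2 continues 8-weekly efficacy follow-up for patients who stopped drug without progression, and ends it at progression or new anticancer therapy, among other reasons.

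**How OS is analysed.** SAP 6.1: "The Safety Analysis Set will be used for overall survival analysis and safety analyses". SAP 6.3.2: "The tables for OS and OS-6m will be summarized in SAF". SAP 8 lists this as a deliberate change: "OS analyses will be conducted in SAF instead of Efficacy Evaluable Analysis Set". (SAP 8 also drops the 6-month OS analysis, which does not alter this point.) SAP 6 covers both phases: "Efficacy and safety analyses will be performed by dose escalation and dose expansion phases accordingly". For escalation it adds: "Within dose escalation phase, data will be summarized by dose level within a dosing cohort or all combined". The censoring rule in SAP 6.3.2 is: "Data from patients who are alive on or before the data cutoff date will be censored at the last known alive date". The SAP gives no rule for how that date is obtained.

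**The concern.** Kaplan-Meier OS assumes that a patient censored at a given time has the same prospects as those still under observation. If an escalation patient's last required contact falls shortly after progression, that assumption is doubtful. The patients leaving the risk set are those whose disease has just progressed, and the curve is then carried mainly by patients who have not progressed.

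At stake is how far the escalation OS tables, by dose level or combined, can be interpreted. There is a practical problem even without bias. Two current passages give sites different instructions for collecting a secondary endpoint, so ascertainment could differ between sites, and survival data not collected at the time may be hard to recover.

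**Working it through.** **Step 1: the passages side by side.**

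| Place | Survival follow-up |
|---|---|
| Protocol 8.5.3 | Names expansion patients |
| Appendix 1 Table 1, footnote 5 | All patients, every 3 months until death |
| Appendix 1 Table 1, column labels | Pre-Screening column marked expansion only; Survival Follow-Up column carries no such mark |
| Protocol 4.1 | Not limited by phase, but defers to 8.5 |
| Synopsis | Not limited by phase |
| Protocol 8.7 | Not limited by phase |

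Section 8.5.3 and footnote 5 cite each other, so neither settles the matter.

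**Step 2: last required contact for an escalation patient if 8.5.3 governs.** For a patient who stops at progression it is the safety follow-up, about 30 days after last dose. For a patient who stops earlier for another reason, efficacy follow-up continues, but it too ends at progression or new therapy. In both cases the last known alive date is tied to progression unless later information happens to arrive.

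**Step 3: possible size.** The documents give no expected OS, event count or hazard, so there is no figure to reproduce. The following are assumptions, not document values:
- median PFS m₁ of 3 to 6 months
- share f of PFS events that are deaths, 10% to 30%
- median post-progression survival m₂ of 4 to 13.3 months
- data cutoff 18 to 36 months after first dose
- contact ending 37 days after progression (30 days plus a 7-day allowance), with no later deaths recorded

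With exponential times, the death hazard is f·ln2/m₁ before progression and ln2/m₂ after it, so the ratio after/before is m₁/(f·m₂). Each row simulates 400,000 patients.

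| m₁ / f / m₂ | Hazard ratio after/before | Median OS, full follow-up | Median OS, contact stops | Ratio of medians |
|---|---|---|---|---|
| 3 / 10% / 4 | 7.5 | 7.8 | 13.1 | 1.68 |
| 4 / 10% / 6 | 6.7 | 11.1 | 21.1 | 1.90 |
| 4 / 20% / 6 | 3.3 | 10.2 | 15.1 | 1.48 |
| 4 / 10% / 9 | 4.4 | 13.9 | 25.5 | 1.83 |
| 6 / 10% / 8 | 7.5 | 15.7 | 35.3 | 2.25 |
| 4 / 30% / 10 | 1.3 | 11.6 | 12.7 | 1.09 |
| 4 / 30% / 13.3 | 1.0 | 13.3 | 13.4 | 1.01 |

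Across these rows, 37 to 48 deaths per 50 patients are seen with full follow-up and 9 to 18 when contact stops. In three scenarios rerun at n = 50 with contact stopping, the median was not reached in 19% to 46% of trials.

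**Step 4: hand check of the second row.**
- Overall PFS hazard: ln2/4 = 0.1733. Progression hazard: 0.9 × 0.1733 = 0.1560. Death hazard before progression: 0.1 × 0.1733 = 0.0173. Death hazard after: ln2/6 = 0.1155. Window w = 37/30.4375 = 1.216 months.
- True survival: S(t) = e^(−0.1733t) + [0.1560/(0.1733 − 0.1155)]·(e^(−0.1155t) − e^(−0.1733t)). This reaches 0.50 at t = 11.1.
- With contact stopping, the ratio of progressed to unprogressed patients at risk settles at A = 0.1560·(e^(0.0578w) − 1)/0.0578 = 0.196. The progressed share is 0.196/1.196 = 0.164.
- The hazard that Kaplan-Meier then sees is 0.836 × 0.0173 + 0.164 × 0.1155 = 0.0334, giving a median of about ln2/0.0334 = 20.7 months. The hazard is lower during the first 37 days, which lifts the median slightly, in line with the simulated 21.1.

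**Step 5: if later deaths are partly learned of.** Suppose half the later deaths become known and everyone else is censored at last contact. In row order the medians become 8.7, 12.1, 10.9, 13.9, 16.9, 11.1 and 11.8. The first five are equal to or slightly above the full-follow-up values; the last two fall below. If all later deaths become known but survivors are still censored at last contact, the medians are 7.8, 10.7, 9.9, 12.4, 14.4, 10.5 and 11.3, which are equal to the true values or too short.

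**The case against.** A reader might infer that the protocol has settled on following expansion patients only, and that escalation OS is therefore certain to be biased upward. The documents do not support that. One section names expansion patients. Footnote 5, the unmarked Survival Follow-Up column, Section 4.1, the synopsis and Section 8.7 all read more broadly. Section 8.6 does not list completion of safety follow-up as a reason for ending participation, and Section 11.2.2 plans to summarise alive or dead status at data cutoff. On balance the text leans towards following everyone. All of this stands, and it makes the point an internal contradiction, not a settled design.

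It is equally fair that upward bias needs more than the literal reading of 8.5.3. The death hazard must rise after progression, and later deaths must go largely unrecorded. The equal-hazard row shows no bias, and step 5 shows that partial capture can remove or reverse it. Section 8.5.4 provides for contacting relatives and referring physicians and for public-record searches. That safeguard is limited: it serves to obtain follow-up that the protocol requires, and under a literal 8.5.3 nothing is required of an escalation patient past progression.

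Finally, little depends on escalation OS. It is secondary and descriptive, there is no hypothesis test, and dose selection rests on DLTs and other escalation data. With about 50 patients spread over two arms and several dose levels, dose-level medians would be unstable even with complete follow-up. That also stands and keeps the point modest. It does not remove the need for the two passages to agree.

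**Conclusion.** The contradiction between Section 8.5.3 and footnote 5 is real and in current text, and the SAP's choice of analysis set makes it matter: OS is planned in patients whom one of the two passages does not follow. If 8.5.3 is applied literally, escalation censoring is tied to progression. Escalation OS would then likely be too long, on the two conditions that the death hazard rises after progression and that later deaths are largely not captured.

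The size cannot be derived from the documents. Under the assumed hazards, with no later deaths captured, the median ranges from unbiased (13.3 against 13.4 months) to about twofold too long (at most 35.3/15.7 = 2.25). With capture of later deaths the error can vanish or change sign. The effect is confined to a descriptive secondary endpoint in about 50 of the planned 250 patients. Expansion-cohort OS is unaffected, because the SAP summarises expansion by cohort and every version of the follow-up text covers those patients.

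**What to change.** Make Section 8.5.3 and footnote 5 agree.
- **If all patients are to be followed:** state that in 8.5.3. The added work is the 3-monthly calls that footnote 5 already describes.
- **If only expansion patients are to be followed:** correct footnote 5, align Section 4.1 and the synopsis, and restrict the SAP's OS analysis to the expansion phase. Alternatively, keep the escalation table and label it as not systematically followed for survival. This costs only a wording change.

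In either case the SAP should say how the last known alive date is obtained and apply the same contact cut to deaths and survivors, since step 5 shows that recording late deaths without updating survivors makes OS too short.
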